6.1 Treatments Administered

6.1.1 Dosing and Duration of Treatment

Acalabrutinib treatment should be administered within 6 hours of randomization on Day 1.

Subjects will take acalabrutinib 100 mg capsules by mouth bid for 10 days (a maximum of 20 doses). Capsules will be taken with water. The capsules should be swallowed intact and subjects should not attempt to open capsules or dissolve them in water. For subjects requiring a proton-pump inhibitor (PPI), acalabrutinib must be administered as described in Section 6.1.3.1.

Acalabrutinib can be taken with or without food.

Retreatment with acalabrutinib is not allowed.

BSC will be administered in both arms per Investigator's discretion and institutional guidelines.

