8.6.2 Time Period and Frequency for Collecting AE and SAE Information

After the signing of the ICF, all SAEs must be reported. After randomization, all AEs/SAEs, irrespective of attribution of causality, must be reported.

AE reporting, irrespective of seriousness, ends 28 (\pm 3) days after the last dose of study treatments(s) for those on acalabrutinib + BSC (Arm 1) and 38 (\pm 3) days from randomization for those on BSC only (Arm 2).

SAEs considered related to study treatments(s) or study procedures occurring after the end of the AE reporting period (as defined above) must be reported. Information on concomitant medications at the time of the treatment-related SAE will also be collected.

All SAEs will be recorded and reported to the Sponsor or designee within 1 day (ie, immediately but **no later than 24 hours** from when he or she becomes aware of it), as indicated in Appendix B. The Investigator will submit any updated SAE data to the Sponsor within 24 hours of it being available.

The method of recording, evaluating, and assessing causality of AE and SAE and the procedures for reporting SAEs are provided in Section 8.7.1.

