9.6 Statistical Analyses

A comprehensive SAP will be developed and finalized before database lock and will describe the subject populations to be included in the analyses, and procedures for accounting for missing, unused, and spurious data. Any deviations from the SAP will be reported in the Clinical Study Report.

The primary analysis of the study will take place when all randomized subjects have been followed for 38 (\pm 3) days from randomization.

An updated analysis for those endpoints requiring 90-day assessments will take place after the last randomized subject has had 90 days follow up from randomization.

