3.2.1 Adverse events

After the signing of the ICF, all SAEs must be reported. After the first dose of study treatment, all AEs/SAEs, irrespective of attribution of causality, must be reported. AE reporting, irrespective of seriousness, ends 28 (± 3) days after the last dose of study treatments(s) for those on acalabrutinib + BSC (Arm 1) and 38 (± 3) days from randomization for those on BSC only (Arm 2).

The following are NOT considered an AE:

- **Pre-existing condition that has not worsened:** A pre-existing condition (documented on the medical history eCRF) is not considered an AE unless the severity, frequency, or character of the event worsens during the study period.
- **Diagnostic testing and procedures:** Testing and procedures should not be reported as AEs or SAEs, but rather the cause for the test or procedure should be reported. If a test or procedure is done to rule out a diagnosis, the sign or symptom leading to the test/procedure should be the event term, and the event term should only be updated to the diagnosis if/when the diagnosis is confirmed. Testing and procedures performed solely as screening measures (e.g., routine screening mammography or colonoscopy) should not be reported as AEs or SAEs.
- **Abnormal laboratory results:** Abnormal laboratory results are not AEs unless they are clinically significant. For example, a clinically significant laboratory result is one that requires treatment (for example a blood transfusion for low haemoglobin) or requires a change in study drug (e.g., lowering the dose or withholding study drug while the laboratory finding resolves or stabilizes).
- **Progression of underlying disease:** Progression of underlying disease unequivocally related to COVID-19 pneumonia (such as worsening of respiratory status or complications associated with pneumonia) will not be reported as an AE if it is clearly consistent with the suspected progression of the underlying disease. Clinical symptoms of progression may be reported as AEs if the symptoms cannot be determined as exclusively due to the progression of the underlying disease, or if

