4.4.1 Adverse events

Verbatim descriptions of AEs will be mapped per version 23.0 of the MedDRA thesaurus terms and graded per National Cancer Institute (NCI) CTCAE, v5.0 or higher. Unless stated otherwise, only treatment-emergent adverse events (TEAEs) will be presented in the summaries. For acalabrutinib + BSC subjects, TEAEs are AEs starting or ongoing AEs worsening after the first dose of study treatment and AEs with start date up to the last dose of study treatment plus 28 (±3) days; for BSC only subjects, TEAEs are AEs starting or ongoing AEs worsening after date of randomization and AEs with start date up to 38 (± 3) days after randomization. In the case a subject's actual treatment received is different than their randomized treatment, TEAEs are AEs starting on or after the date of randomization up to the later of 38 (± 3) days after randomization or the last dose of study treatment plus 28 (±3) days. When programmatically assigning the AEs as treatment emergent, the upper window will be used.

The following summaries will be provided:

- A summary of the number and percentage of subjects reporting any TEAE, TEAEs with outcome of death, at least one TEAE of CTCAE grade 3 or higher, at least one serious TEAE, at least one TEAE possibly related to study drug, and at least one TEAE leading to discontinuation of study drug by treatment group.
- A summary of the number of TEAEs, TEAEs with outcome of deaths, TEAEs with CTCAE grade 3 or higher, serious TEAEs, TEAEs possibly related to study drug, and TEAEs leading to discontinuation of study drug by treatment group.
- A summary of the number and percentage of subjects reporting a TEAE by treatment group, SOC and PT.
- A summary of the number and percentage of subjects reporting the most common TEAEs (occurring in at least 5% of overall subjects) by treatment group, SOC and PT.
- A summary of the number and percentage of subjects reporting a TEAE by treatment group, CTCAE grade, SOC and PT. This will include a subset of grade 3 or higher.
- A summary of the number and percentage of subjects reporting a TEAE possibly related to study drug by SOC and PT.
- A summary of the number and percentage of subjects reporting a TEAE leading to discontinuation of study drug by SOC and PT.

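### The adverse-event window runs from last dose in Arm 1 but from randomization in Arm 2, so Arm 1 subjects who stop early lose up to 10 of 41 days of AE counting

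*SAP*

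**What the plan says.** SAP 4.4.1 sets two end points for TEAEs. For acalabrutinib plus BSC it takes "AEs with start date up to the last dose of study treatment plus 28 (±3) days"; for BSC alone it takes "AEs with start date up to 38 (± 3) days after randomization". Protocol 9.6.1 has the same pair. The SAP then states: "When programmatically assigning the AEs as treatment emergent, the upper window will be used". The programmed limits are therefore last dose + 31 days and randomization + 41 days.

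Collection follows the same split. Protocol 8.6.2 says "AE reporting, irrespective of seriousness, ends 28" (±3) days after last dose in Arm 1, and 38 (±3) days from randomization in Arm 2. SAP 3.2.1 repeats this, and the safety follow-up visit in protocol 4.5 and 7.1 is timed the same way.

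SAP 4.4.1 has a common rule from randomization only for subjects whose actual treatment differs from the randomized one: "TEAEs are AEs starting on or after the date of randomization up to the later of 38" (±3) days after randomization or last dose plus 28 (±3) days. Arm 1 subjects who never take acalabrutinib move to the BSC group (SAP 2.1.3). No rule covers an Arm 1 subject who takes at least one dose and then stops.

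The start of collection also differs between documents. Protocol 8.6.2 starts full AE collection at randomization. SAP 3.2.1 says: "After the first dose of study treatment, all AEs/SAEs, irrespective of attribution of causality, must be reported".

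**The concern.** Safety is one of the two primary objectives. The SAP 4.4.1 tables give numbers and percentages of subjects with TEAEs, and raw TEAE counts, by treatment group, with no adjustment for time at risk. Such tables compare like with like only if both arms are observed for the same length of time, or if any difference has nothing to do with outcome.

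Neither condition is guaranteed here. Protocol 6.1.3.3 ends treatment when a subject can no longer swallow the capsules, protocol 7.1 lists AEs among the reasons to stop, and the table in protocol 6.7 names toxicities that lead to discontinuation. Each of these moves the last dose earlier and so closes the Arm 1 window earlier. Arm 2 has no last dose, so its window cannot shrink in this way.

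The gap cannot be repaired fully at analysis, because routine collection stops on the same clock. The listing of all AEs can show only what was collected.

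**Working it through.** **Inputs**
- Arm 1 window end: last dose + 28 days, + 3 as programmed (SAP 4.4.1).
- Arm 2 window end: randomization + 38 days, + 3 as programmed (SAP 4.4.1).
- Planned dosing: "Subjects will take acalabrutinib 100 mg capsules by mouth bid for 10 days (a maximum of 20 doses") (protocol 6.1.1).
- On-schedule last dose: Day 10, or Day 11 if the first dose is in the evening (SAP 3.2.2).
- Day 1 is the date of randomization (SAP 4.1), so a last dose on Day d falls at randomization + (d − 1).

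**The plan's own figure.** 10 days of dosing + 28 = 38. This is exact for a last dose on Day 11 (10 + 28 = 38) and one day out for Day 10 (9 + 28 = 37). The 38-day figure therefore reproduces for subjects who complete dosing on schedule.

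**Window end by day of last dose.** Arm 1 end = (d − 1) + 31; Arm 2 end = 41.

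| Last dose | Arm 1 end (from randomization) | Difference from Arm 2 |
|---|---|---|
| Day 1 | +31 | −10 days (10/41 = 24%) |
| Day 4 | +34 | −7 days (7/41 = 17%) |
| Day 7 | +37 | −4 days |
| Day 10 | +40 | −1 day |
| Day 11 | +41 | 0 |
| Day 13 or 14, after a 3-day hold with make-up doses | +43 or +44 | +2 or +3 days |

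The 3-day tolerance is added in both arms and cancels: without it, a Day 1 last dose ends at +28 against +38, still 10 days short. The asymmetry comes from the two anchors, not from the choice of the upper limit. For a Day 1 stopper the lost days are randomization +32 to +41.

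**Possible size at arm level.** The documents give no early-stopping rate, so the following rests on assumptions. Let a fraction f of Arm 1 stop on Day d, and let the rest average 40.5 days.

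Ratio of window days, Arm 1 to Arm 2 = [(1 − f) × 40.5 + f × (d − 1 + 31)] / 41
- f = 10%, Day 5: (36.45 + 3.5) / 41 = 0.974
- f = 40%, Day 1: (24.3 + 12.4) / 41 = 0.895
- f = 0: 40.5 / 41 = 0.988

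Now assume also a constant hazard and a 50% chance of at least one TEAE in 41 days. The chance that a stopper has a counted TEAE is 1 − 0.5^(window/41).
- Day 1 stopper: 1 − 0.5^(31/41) = 0.408, a shortfall of 0.092
- Day 5 stopper: 1 − 0.5^(35/41) = 0.447, a shortfall of 0.053

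Across the arm, early stopping would lower the percentage of subjects with a TEAE by 0.10 × 0.053 = 0.5 points (10% stop on Day 5) to 0.40 × 0.092 = 3.7 points (40% stop on Day 1). One subject in an arm of 30 is 1/30 = 3.3 points.

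**Check on a Day 28 cut.** The earliest nominal end of Arm 1 collection is (1 − 1) + 28 = randomization + 28. The schedules of activities also place an AE assessment at Day 28 (±3) in both arms. A table cut at Day 28 therefore falls within planned collection for every dosed subject.

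**The case against.** The strongest reply is that the effect is small and partly covered elsewhere, and much of that stands. The missing days are the tail of the window only. AEs are assessed in both arms at Days 14 and 28. Protocol 8.6.10 keeps events unequivocally due to COVID-19 pneumonia out of AE reporting (protocol 8.6.9 is less absolute for serious events), so much of the deterioration that ends dosing would not be in the TEAE tables anyway. Related SAEs after the window must still be reported (protocol 8.6.2). Total deaths and Day 90 mortality are summarized regardless of the window (SAP 4.4.1.1 and 4.3.2.5). Safety is descriptive, without tests. The SAP amendment history also shows that the 38-day point was chosen to bring Arm 2 closer to Arm 1.

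That choice works for completers. It does nothing for early stoppers, and unrelated or non-serious late events in them are neither collected nor counted.

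Three stronger readings are tempting but not supported:
- **Early stoppers are often the sickest subjects, so the tables mostly favour acalabrutinib.** The documents give a mechanism but no frequency, and the order of reasons in protocol 7.1 is not a ranking. Make-up doses (protocol 6.1.2) lengthen some Arm 1 windows.
- **The different start points bias the comparison.** Treatment should start within 6 hours of randomization, so the gap is hours. The SAP 3.2.1 wording is a mismatch to correct: study treatment means acalabrutinib (protocol 6), so the rule does not fit BSC subjects, but protocol 8.6.2 already starts their collection at randomization.
- **The primary lock cuts off Arm 1 windows.** Protocol 9.6 states: "The primary analysis of the study will take place when all randomized subjects have been followed" for 38 (±3) days. Only a subject randomized in the last few days who also used make-up doses could have a window (up to randomization +43 or +44) still open then.

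**Conclusion.** The point holds for Arm 1 subjects who take at least one dose and stop before about Day 10. They lose up to 10 of 41 days (24%), all in the late tail, and that maximum needs a single day of dosing. Completers lose 0 to 1 day. The shortening can occur in one arm only and can follow from toxicity or deterioration, so where late events are missed the Arm 1 count is too low.

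The net effect on the trial cannot be fixed from the documents. Under the assumptions above (10% to 40% stopping between Day 1 and Day 5, constant hazard, 50% TEAE risk over 41 days), early stopping lowers the Arm 1 percentage by about 0.5 to 3.7 points, at most roughly one subject in 30. If events cluster early in the illness, the effect would be smaller. This is a modest, avoidable bias in a primary safety comparison. It is worth correcting because the remedy is cheap and SAP 4.4.1 already counts from randomization for treatment-discordant subjects. It does not invalidate the safety analysis.

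**What to change.** 1. For between-arm AE summaries, define one fixed window for both arms in SAP 4.4.1 and protocol 9.6.1: randomization to 38 days after it, upper limit 41.
2. Collect AEs to that point for Arm 1 subjects who stop early, with matching changes in protocol 4.5, 7.1 and 8.6.2, SAP 3.2.1 and the Arm 1 schedule of activities.
3. Tabulate separately any Arm 1 events after randomization + 41 but within last dose + 31 days. Extending the existing later-of-two-dates rule to everyone would not do, since Arm 1 subjects with make-up doses would then have longer windows than Arm 2.
4. Recruitment was complete at 62 subjects when SAP version 3.0 was written, so later contact may no longer be possible for some. In that case add a by-arm AE table truncated at Day 28 after randomization, which needs no new data.
5. Change the start of AE collection in SAP 3.2.1 to randomization, as in protocol 8.6.2.

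Cost: one later telemedicine contact per early stopper, the matching wording changes in the protocol and SAP, and one extra table.

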4.4.1.1 Deaths, serious adverse events (SAEs), and other significant adverse events

The following summaries will be provided:

- A summary of the number and percentage of total deaths, deaths related to the disease under investigation (as determined by the investigator), deaths after the end of safety follow-up (28 (\pm 3) days after last dose for acalabrutinib + BSC subjects, 38 (\pm 3) days after randomization for BSC only subjects) by treatment group

- A summary of the number and percentage of subjects reporting a treatment-emergent SAE by treatment group, SOC and PT.
- A summary of the number of treatment-emergent SAEs by treatment group, SOC and PT.
- A summary of the number and percentage of subjects reporting a treatment-emergent SAE leading to discontinuation of study drug by SOC and PT.
- A summary of the number and percentage of subjects with a treatment-emergent SAE with an outcome of death by treatment group and PT.

Adverse events of special interest (AESI) for acalabrutinib include ventricular arrhythmias (e.g., ventricular extrasystoles, ventricular tachycardia, ventricular arrhythmia, ventricular fibrillation). AESI PTs are listed in Section 8.1. These events will be summarized as follows:

- A summary of the number and percentage of subjects reporting an AESI by treatment group, CTCAE grade, group term and PT.
- A summary of the number and percentage of subjects reporting an AESI possibly related to study drug by group term and PT.
- A summary of the number and percentage of subjects reporting an AESI leading to discontinuation of study drug by SOC and PT.

A list of AESI PTs will also be provided.

Events of clinical interest (ECIs) are provided in Section 8.1. ECIs will be reported for the duration of study treatment and during any protocol-specified follow-up period. These events will be summarized similarly to AESIs by treatment group and a list of ECI PTs will be provided.

The following by-subject listings will be presented:

- A by-subject listing of key information for serious adverse events (SAEs).
- A by-subject listing of key information for AESIs and ECIs.
- A by-subject listing of deaths, including the date of death, the primary and secondary cause of death, whether an autopsy was performed and whether the death was related to the disease under study.
- A by-subject listing of key information for AEs leading to discontinuation of study treatment.

The following subject narratives will be provided:

- Narratives of SAEs with an outcome of death.
- Narratives of SAEs, possibly related to study drug.

- Narratives of discontinuation of investigational product due to AEs.
- Narratives of AESIs.
- Narratives of any other medically-relevant AE that does not fall into the above categories.

No formal statistical tests will be performed to compare AE rates between treatment groups.

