9. STATISTICAL CONSIDERATIONS

9.1 Statistical Hypotheses

Overall study design is described in Section 4.1 of the protocol. Subjects who are hospitalized for COVID-19 symptoms and meet the eligibility criteria will be randomized 1:1 to receive acalabrutinib plus BSC (Arm 1: n=30) vs BSC (Arm 2: n=30).

Stratification by age (≥ 65 vs < 65 years) and comorbidities (present vs absent) will be applied to randomization.

The primary objective of the study is to evaluate the safety and preliminary efficacy of acalabrutinib plus BSC (Arm 1) vs BSC (Arm 2). There is no formal hypothesis testing for the safety and efficacy endpoints. The primary focus for the efficacy is to estimate the treatment effect as measured by the difference between treatment arms in the proportion of subjects who are alive and free of respiratory failure.

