3.2 Safety variables

The safety of acalabrutinib in subjects with COVID-19 when administered with BSC is a primary endpoint and will be assessed by type, frequency, severity, and relationship to study treatment of any treatment-emergent adverse events (TEAEs) or abnormalities of laboratory tests, serious adverse events (SAEs), or adverse events leading to discontinuation of study treatment.

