4.4 Analysis of safety

This section describes safety analyses to be conducted. All of the analyses in this section will be based on the safety population and will be performed for all safety variables specified below. All analyses of safety data will employ descriptive statistics. Formal statistical analysis (with generation of a p-value) will not be performed for these endpoints.

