For the most common TEAEs, all events that occur in at least 5% of subjects overall will be summarized by preferred term, by decreasing frequency. This cut-off may be modified after review of the data. When applying a cut-off (e.g., 5%), the raw percentage should be compared to the cut-off, no rounding should be applied first (i.e., an AE with frequency 4.9% will not appear if the cut-off is 5%).

The following by-subject listings will be provided:

- A listing of all AEs (including non-treatment-emergent events and any collected but are not, by definition, AEs since they are related to disease under study), by treatment group, and including center, E-code, AE (SOC, PT, verbatim term), date of onset, date of resolution, duration, CTCAE grade, seriousness, action taken, outcome, relationship to study treatment and time from last dose to start of AE.

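### Safety is a primary objective, yet the SAP plans no between-arm difference or interval for any safety outcome, so the output will not show how large an excess equal columns leave open

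*SAP*

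**What the plan says.** Safety and efficacy are both listed as primary objectives (Protocol 3; SAP 1.1.1), and SAP 3.2 says: "The safety of acalabrutinib in subjects with COVID-19 when administered with BSC is a primary endpoint".

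On analysis, SAP 4.4 says "All analyses of safety data will employ descriptive statistics" and "Formal statistical analysis (with generation of a p-value) will not be performed for these endpoints". SAP 4.4.1.1 closes with "No formal statistical tests will be performed to compare AE rates between treatment groups". The outputs in SAP 4.4 to 4.4.6 are counts, percentages, summary statistics, shift tables, listings and narratives.

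For efficacy, Protocol 9.1 says: "The primary focus for the efficacy is to estimate the treatment effect as measured by the difference between treatment arms". SAP 4.3.1.1 gives the primary endpoint a 90% CI in each arm, a difference with a 90% CI, a stratified Cochran-Mantel-Haenszel test, an unstratified chi-square test and a logistic regression estimate.

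One AE summary in SAP 4.4.1 is restricted to the "most common TEAEs (occurring in at least 5% of overall subjects) by treatment group, SOC and PT". The percentage is compared with 5% unrounded, and "This cut-off may be modified after review of the data".

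**The concern.** The trial has a concurrent randomized control, and Protocol 6.6 says that acalabrutinib's safety profile in COVID-19 is not yet established. A reader will compare the two AE columns whether or not the SAP does so. With about 31 subjects per arm the comparison is imprecise. A table of bare percentages does not show that, so two similar columns could be taken as reassurance when the data are compatible with a sizeable excess on acalabrutinib. The protocol states the expected precision of the efficacy difference but gives no such figure for safety.

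A smaller matter is the common-TEAE table. It is shown by arm, but its rows are chosen on the pooled percentage, with a threshold that may move once the data have been seen.

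**Working it through.** **Inputs.** 62 randomized (SAP 1.3), planned 60 (Protocol 9.2), 1:1 allocation, 90% level as used for efficacy. Assumed: all 62 are in the safety set, split 31 to 31. The documents give only the total.

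**The plan's own precision figure (efficacy, 30 per arm, 70% vs 90%).**
- Half-width = 1.645 × √(0.7×0.3/30 + 0.9×0.1/30) = 1.645 × 0.100 = 16.4 points, as stated.
- Power = Φ(0.20/0.100 − 1.645) = Φ(0.355) = 64%, as stated.

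**What equal safety columns exclude.** The Newcombe interval combines each arm's Wilson limits (l, u). When the arms are equal the difference is 0 ± √[(p − l)² + (u − p)²].
- 0/31 vs 0/31: l = 0, u = z²/(31 + z²) = 2.706/33.706 = 0.080, giving ±8.0 points.
- 3/31 vs 3/31: p = 0.097, l = 0.039, u = 0.219, giving √(0.0574² + 0.1222²) = ±13.5 points.
- 6/31 vs 6/31: p = 0.194, l = 0.104, u = 0.333, giving √(0.0900² + 0.1392²) = ±16.6 points.

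For an unequal pair, 3/31 vs 0/31 gives 9.7 points (−0.2 to 21.9).

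**The 5% cut-off.**
- Pooled rule at 62: 0.05 × 62 = 3.1, so 4 subjects in total are needed. An event in 3/31 vs 0/31 (9.7% vs 0%) is 3/62 = 4.84% and is left out. At 60 subjects, 0.05 × 60 = 3, so 3 vs 0 would be kept and 2 vs 0 left out.
- Either-arm rule at 31: 0.05 × 31 = 1.55, so 2 subjects in one arm are enough.

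Chance that an event enters the table (31 per arm):

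| True incidence, acalabrutinib / BSC | Pooled rule | Either-arm rule |
|---|---|---|
| 10% / 0% | P(Bin(31, 0.10) ≥ 4) = 38% | P(Bin(31, 0.10) ≥ 2) = 83% |
| 15% / 0% | 70% | 96% |
| 5% / 5% | P(Bin(62, 0.05) ≥ 4) = 38% | 1 − P(Bin(31, 0.05) ≤ 1)² = 71% |
| 3% / 3% | 12% | 42% |

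The either-arm rule picks up more one-sided events, but part of the gain comes simply from a lower threshold, and it admits more balanced events as well.

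**The case against.** Descriptive safety reporting without tests is a declared and ordinary choice in a Phase 2 trial of this size. It agrees with Protocol 9.1, which disclaims formal hypothesis testing for safety and efficacy alike. That stands: there is no contradiction between the documents, and this point asks for no test.

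Nor is safety alone in lacking a contrast. Day 90 mortality gets a Kaplan-Meier estimate in each arm only, and the day-count endpoints get summaries by arm. Those are secondary endpoints, however, and safety is primary.

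The requested difference also has limits. SAP 2.1.3 groups subjects as treated, so a subject randomized to acalabrutinib who never takes it counts under BSC, and the contrast is not strictly randomized. The TEAE windows differ too (first dose to last dose plus 28 days, against randomization to Day 38, each ±3 days) and diverge if dosing stops early. Several unadjusted intervals need a statement of how to read them. These are reasons to label the intervals carefully, not to omit them.

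Three stronger readings are tempting but unsupported:
- **That the pooled cut-off is built to favour balanced events over one-sided ones.** It depends only on the total count: 4 vs 0 and 2 vs 2 are both shown, and 3 vs 0 and 2 vs 1 are both left out.
- **That safety signals are hidden.** The TEAE table by arm, SOC and PT, the CTCAE-grade table, the SAE, AESI and ECI tables and the full AE listing have no cut-off.
- **That the SAP concludes safety from similar columns.** It sets no such rule. The misreading is a risk for readers of the report.

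It would also be wrong to say that efficacy is estimation-only, since SAP 4.3.1.1 plans two tests.

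**Conclusion.** The point holds as a worthwhile, inexpensive improvement rather than the correction of an error. A primary objective of a randomized trial is reported without any between-arm estimate or interval. Identical columns would leave open an excess of about 8 to 17 points when 0 to 6 subjects per arm have the event, and no planned output would say so. This rests on a 31 to 31 split with everyone in the safety set, and on Newcombe intervals at the 90% level used for efficacy.

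The cut-off issue is secondary. At 62 subjects it affects events seen in at most 3 subjects in total, in one summary table.

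**What to change.** 1. In SAP 4.4.1 and 4.4.1.1, add the unadjusted risk difference (acalabrutinib + BSC minus BSC, safety set as treated) with a 90% score-type CI (Newcombe or Miettinen-Nurminen, one method named in advance) and no p-value. Restrict it to a fixed list:
   - any TEAE of Grade 3 or higher
   - any serious TEAE
   - any fatal TEAE
   - the ventricular arrhythmia AESI
   - the major hemorrhage ECI
   - the infections ECI
2. State beside the table that the intervals are descriptive and not adjusted for multiplicity, that subjects are grouped as treated, and that the TEAE windows differ by arm.
3. In SAP 4.4.1, delete "This cut-off may be modified after review of the data" and apply the 5% cut-off to either arm instead of to all subjects pooled.

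The cost is SAP wording and one extra table. It needs no new data and no tests. Several of the intervals will be wide, and that is the information now missing. The common-TEAE table becomes longer and takes in more balanced low-frequency events (at a true 5% in both arms, inclusion rises from 38% to 71%).
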